A sample size of 12 per group provides 80% power to detect a 50% difference in proportions of participants between groups by chi2 test experiencing a laboratory abnormality or adverse event at a significance threshold of α =0.05. In addition, based on our preliminary trial data for change in TNF- α , and applying a 2-sided t-test of means, n=24 allows for n=12 per arm and provides >90% power, at a significance threshold α =0.05, to detect a mean change of -0.5 =/- 0.25 pg/ml in XN-treated participants with CD, based on an estimated mean change of 0.1 +/- 0.25 pg/ml from placebo. Will we randomize up to 32 participants to allow for attrition up to 25% [resulting in a final sample of at least n=24/arm.

Based on our preliminary trial data for change in TNF- α , and applying a 2-sided t-test of means, n=24 allows for n=12 per arm and provides >90% power, at a significance threshold α =0.05, to detect a mean change of -0.5 =/- 0.25 pg/ml in XN-treated participants with CD, based on an estimated mean change of 0.1 +/- 0.25 pg/ml from placebo. Will we randomize up to 32 participants to allow for attrition up to 25% [though we had <10% attrition in our previous trial in this population] resulting in a final sample of at least n=24/arm.

15 Recruitment

Participants will be recruited from the region via posted fliers and the NUNM clinic via posted fliers and IRB-approved mailings to current patients. Members of the study team will present information about study participation to CD support and community groups and set out flyers for attendees to pick up. In addition, we will use Craigslist and social media (i.e. Facebook and Instagram) as well as the NUNM weekly newsletter. Candidates from the community would

simply respond to a dedicated study telephone line or email, and express their interest, and are then contacted by a Study Coordinator.

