Given the small sample size of these clinical trials, results related to changes in inflammatory cytokines (IL-1 β , IL-2, IL-6, IL-8, IL-10, TNF- α , and IL-12p70), gut permeability biomarkers (CD14, intestinal fatty acid binding protein) and markers of endotoxemia (LPS, LPS-binding protein) are considered preliminary, and thus our principle assessment will be measurement of effect size as *Cohen's d* statistic between XN- and placebo-treated groups at each 2-week interval compared to baseline, with the primary comparison being between baseline and week 8. We will also perform formal statistical comparisons as unpaired, 2-sided t-tests (or, if inspection of distributions indicates strong non-normality, with a non-parametric Wilcoxon signed rank test) of the means at relevant time points. The following findings will be considered evidence of possible effects: 1. Clinically and statistically significant effects for changes in cytokines of interest and/or 2. Calculation of a Cohen's d value for effect size estimation greater than 0.5 (with larger d indicating a larger potential effect size).

Assessment for overall *increases* or *decreases* in parameters of interest will be tested for linear trends of the means by linear mixed ANOVA with time point as a repeated factor. Trends will be considered significant if p<0.05 for the model overall.

Analysis of XN, its metabolites, and BAs to determine a small molecule signature of longer-term oral treatment with XN:

We will identify and quantify XN and XN-derived metabolites in plasma, stool, and urine samples. Bile acid profiles will also be determined in the stool samples. The metabolite profile data will then be used for correlation with the time-resolved gut microbiome analysis. This approach will allow us to determine links between metabolite profiles and gut microbiome compositions.

Protocol

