provides genome-centric resolution by integrating genome binning. The full ATLAS protocol is developed and maintained as open-source software on GitHub and is implemented in Snakemake for modular, flexible, and reproducible workflows. Individual protein sequence databases will be created based on a combined metagenome that will serve as references for paired metaproteome analysis. To complement these assemblies and produce as comprehensive an assessment of microbiome structure and functional capacity as possible, we will also conduct analyses at the level of individual, unassembled reads. Specifically, we will analyze quality-controlled metagenomes using MetaPhlan2 to measure the abundance of specific microbial taxa in each metagenome.⁴¹ We will also use ShotMAP to assign reads into KEGG Orthology groups based on homology.³³ Briefly, ShotMAP predicts coding sequences from unassembled metagenomic data using Prodigal and applies RAPsearch or DIAMOND to rapidly identify reads that show evidence of homology to KEGG Orthology groups. Our prior statistical simulations surrounding this technique highlight its accuracy and our prior applications of these tools resolved taxa and microbiome metabolic modules that predict immune activation in mouse models of IBD and flare-ups in IBD patients.^{28,33}

20b Subgroup and/or adjusted analyses.

No subgroup analyses are planned. If significant differences in disease severity (CDAI-measured) become evident between XN- and placebo-treated groups, ANCOVA will be performed for all tests of mean differences (i.e., pro-inflammatory cytokine, gut permeability and endotoxemia-related parameters), adjusting for baseline CDAI score between groups.

20c Methods for imputation and/or consideration of protocol non-adherence.

To evaluate the statistical relevance of missing data, for example when the data is absent in the control group and present in the treatment group, we will utilize a G-test.²⁵ However, with multiple comparisons comes the problem of increased likelihood of a significant result by random chance. To counter this problem, we use either the Dunn-Sidak or Bonferroni correction to adjust p-values.⁴² If the data have a linear relationship, then we use partial least squares discriminant analysis (PLS-DA) and rank the molecules by p-value in a pair-wise comparison to the control group.^{43,44}

Monitoring

21a Data monitoring

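### The week-8 between-arm comparisons use only participants with a week-8 value, so loss that is related to outcome and unequal between arms can bias them in either direction

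*Protocol*

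**What the plan says.** All references are to the protocol.

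- **Section 20a, inflammatory cytokines, gut permeability biomarkers and endotoxemia.** The main assessment is Cohen's d between XN and placebo at each two-week interval, "with the primary comparison being between baseline and week 8". Significance testing is added: "We will also perform formal statistical comparisons as unpaired, 2-sided t-tests", with a Wilcoxon test if the data are strongly non-normal. A d above 0.5 counts as evidence of a possible effect.
- **Section 20a, laboratory toxicology.** Mean laboratory values are compared between arms with unpaired two-sided t-tests.
- **Section 20a, both parts.** Parameters "will be tested for linear trends of the means by linear mixed ANOVA with time point as a repeated factor". For the cytokine and permeability markers the criterion is: "Trends will be considered significant if p<0.05 for the model overall".
- **Section 14.** The plan is to randomise up to 32 participants "to allow for attrition up to 25" per cent, and power is computed for the 24 who remain. The section adds: "though we had <10% attrition in our previous trial in this population".
- **Section 20c.** The heading covers imputation and non-adherence. The text opens "To evaluate the statistical relevance of missing data" and names a G-test, then p-value corrections and a discriminant analysis.

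**The concern.** A week-8 Cohen's d and a week-8 t-test can include only people measured at week 8. A participant who leaves after week 2, 4 or 6 has blood markers on file, but these do not enter the comparison that section 20a calls primary. Nothing in section 20c changes that estimate: a G-test can show that values are missing unevenly, but it does not correct for it.

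The mixed ANOVA does not fill the gap. As described, it tests a linear trend over time and is judged by the p-value of the whole model. It names no arm-by-visit term and no week-8 treatment contrast. Neither of the two criteria that section 20a lists as evidence of a possible effect refers to it.

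What is at stake is the week-8 effect size. If the people who leave differ in outcome from those who stay, and this loss differs between arms, the arms left at week 8 are no longer comparable. The d > 0.5 rule is applied to eleven markers (seven cytokines, two permeability markers, two endotoxemia markers), so modest distortions can decide what is reported as a signal.

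**Working it through.** **1. The protocol's own figures.** From section 14: mean change −0.5 on XN, +0.1 on placebo, SD 0.25 pg/ml, 12 per arm, two-sided α = 0.05.

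- Difference = −0.5 − 0.1 = −0.6, so d = 0.6 / 0.25 = 2.4.
- Noncentral t with df = 22 and noncentrality 2.4 / √(1/12 + 1/12) = 5.88 gives power 0.9999. The stated figure of more than 90% is met.
- 24 / (1 − 0.25) = 32, so the attrition allowance also reproduces. It leaves 24 in total, 12 per arm. The wording in section 14 that 24 per arm remain is a separate slip.

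**2. Simulation of the week-8 comparison.** From the protocol: 32 randomised, visits at weeks 2, 4, 6 and 8, SD 0.25, and 25% loss (8 people). Assumed: 16 per arm, true week-8 difference −0.25 (d = 1) building up linearly, correlation 0.6 between visits, and leaving after week 4 by those with the worst week-4 values in their arm. There were 2,000 runs per setting. Negative values favour XN.

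The comparator fits week 8 on arm, week 2 and week 4 among completers, and averages the predictions over everyone randomised. It stands in for a likelihood model under missing at random; the full mixed model was not fitted.

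| Leavers (placebo / XN) | Completer estimate | Completer power | Estimate using earlier visits |
|---|---|---|---|
| 4 / 4, at random | −0.247 | 64% | −0.247 |
| 4 / 4, worst values | −0.251 | 73% | −0.251 |
| 6 / 2, worst values | −0.198 | 51% | −0.251 |
| 8 / 0, worst values | −0.137 | 24% | −0.251 |
| 2 / 6, worst values | −0.307 | 85% | −0.253 |
| 0 / 8, worst values | −0.366 | 92% | −0.251 |

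With nobody lost, power is about 78–80%.

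- 6 / 2: (0.250 − 0.198) / 0.250 = 21% too small.
- 2 / 6: (0.307 − 0.250) / 0.250 = 23% too large. (Rounding the estimates to two decimals first gives 20% and 24%.)
- 6 / 2 with correlation 0.3: −0.224, or 10% too small. With correlation 0.8: −0.175, or 30% too small.

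**3. No true effect.** The completer t-test rejects in 9% of runs (6 / 2) and 10% (2 / 6), and in 17–18% when all eight leavers come from one arm, against a nominal 5%.

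**4. The d > 0.5 rule.** Here the assumptions are a true difference of 0.8 SD, correlation 0.5–0.7, and loss after week 4 of those who worsened most from baseline. With 6 / 2 loss the completer estimate is 0.63–0.66 SD, and the chance of d > 0.5 falls from 81–93% to 65–82%. With 2 / 6 loss and no true effect, the chance of d > 0.5 in favour of XN rises from about 8–9% to about 24%.

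**5. The planned TNF-α effect.** At −0.60, 6 / 2 loss gives −0.548 and 8 / 0 loss gives −0.488. The estimate shrinks by 9% and 19%, but power stays at or above 99.5%.

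**The case against.** A reader might infer more than this: that leavers' earlier data are thrown away, and that placebo participants leaving with flares will hide a benefit of XN. The documents support neither.

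- **Data are not discarded overall.** Section 20a also plans d at each two-week interval and a mixed ANOVA on the same markers. Earlier visits are lost only from the week-8 contrast.
- **The direction is not known.** The protocol nowhere predicts flare-related dropout on placebo. Section 11d lists glucocorticoids as an allowed emergency intervention, so a flare need not mean leaving. Section 11b withdraws participants for certain gastrointestinal events attributed to the intervention, which could unbalance loss the other way. Balanced outcome-related loss gave no bias here, and about 7% in another simulation in which both arms left after worsening.
- **25% is a ceiling.** Attrition in the earlier trial was under 10%, which would be at most 3 of 32. Section 13b provides for shipped samples, remote blood draws and a higher payment for the week-8 draw. These reduce missed visits, although they do not help once someone has withdrawn.
- **The planned effect is not hidden.** At d = 2.4, detection is practically certain in every setting examined.
- **The scope is limited.** Section 20a states no week-8 t-test for CDAI, C-reactive protein or calprotectin, so the point does not extend to them.
- **Model detail belongs in the SAP.** That is fair for covariance structures and degrees of freedom. But the protocol itself names the week-8 estimator, and its own missing-data section does not repair it.

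The conditional ANCOVA in section 20b is no answer either: it adjusts for baseline CDAI only if the arms differ in severity, and brings no leaver back. All these limits stand, but the core point remains.

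**Conclusion.** The point holds for the week-8 comparison of cytokines, permeability and endotoxemia markers, and for the matching t-tests of mean laboratory values. These use observed cases only, while the protocol allows for losing up to a quarter of participants and names no method that uses leavers' earlier visits in this contrast.

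The possible bias runs in either direction: a little over 20% of the effect for a 6-to-2 split of the eight leavers, on the assumptions of d = 1, correlation 0.6 and leaving on the worst week-4 values. It is smaller with weaker correlation between visits, and little or none if loss is random or balanced. A loss below 10% was not simulated; with fewer leavers the bias should be smaller. The claim that an XN benefit would be hidden is not supported, because the opposite imbalance overstates the benefit and the planned TNF-α effect survives in every setting. This is an improvement worth making, not a fatal flaw.

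**What to change.** In section 20a, take the week-8 XN-minus-placebo difference, and Cohen's d, from a likelihood-based mixed model on all visits:

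- terms for visit, arm-by-visit, baseline value and sex (the factor used in the randomisation);
- everyone randomised who has any post-baseline value;
- small-sample degrees of freedom;
- an unstructured covariance, with a simpler structure stated in advance in case it does not converge. Four post-baseline visits need 4 × 5 / 2 = 10 covariance parameters from 24 to 32 people, so the fallback matters.

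Keep the observed-case t-test as a sensitivity analysis. Add one simple missing-not-at-random check, for example shifting the values assumed for leavers by a range of amounts, separately by arm. Refer to this analysis in section 20c.

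No new data are needed, since the visits and a mixed model are already in the plan. The cost is the revised text and some programming across eleven markers and the laboratory values. The downside is that the model assumes observed data explain dropout, which is why the last check is needed. Its convergence and error rates at this sample size were not tested here.

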Laboratory measures (including red blood cell count, white blood cell count, hematocrit (%), hemoglobin, mean corpuscular volume, AST, ALT, creatinine-estimated glomerular filtration rate (eGFR), blood urea nitrogen (BUN), and creatinine) will be analyzed by first assessing descriptive statistics including mean, median and standard deviation. All distributions will be tested for skew and transformed (e.g., natural log transformed) as needed to reduce the influence of skew in subsequent analyses. All parameters will be evaluated by formally comparing means from baseline

Protocol

to each time point by unpaired, 2-sided t-tests, as well as for trends over time by applying linear mixed ANOVA models with time point as a repeated factor.

As an element of the evaluation for safety of the intervention, the % laboratory newly abnormal (for values within the clinically normal range at baseline) per clinical laboratory reference ranges for each lab parameter will be reported at each 2-week time point and the % compared between XN and placebo groups by Fisher's exact test.

Assessment for changes in the distribution of each lab parameter will be performed by presenting means and confidence intervals (CI) for the change in each group, as well as the mean CI for the difference between groups; significance will be tested using 2-sided, unpaired t-tests (or, if inspection of distributions indicates strong non-normality, with a non-parametric Wilcoxon signed rank test) of the mean values for XN compared to placebo.

Assessment for overall *increases* or *decreases* in parameters of interest will be tested for linear trends of the means by linear mixed ANOVA with time point as a repeated factor, which may be suggestive of evidence for cumulative toxicity if trending in a clinical deleterious direction.

Analysis of inflammatory cytokines, gut permeability biomarkers, and endotoxemia:

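### As worded, the formal cytokine and laboratory tests in section 20a compare visit means, while the section 14 power, the effect size and the evidence rule all concern change from baseline

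*Protocol*

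**What the plan says.** **Section 14 (Sample Size).** For the active arm, the TNF-alpha calculation is set "to detect a mean change of -0.5 =/- 0.25 pg/ml in XN-treated participants with CD". The placebo arm has its own assumption: a mean change of 0.1 with the same spread of 0.25 pg/ml. The method is given as "applying a 2-sided t-test of means, n=24 allows for n=12 per arm", with claimed power above 90% at alpha 0.05. The powered variable is change, compared between arms.

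**Section 20a, cytokine subsection.** The results are called preliminary. The principal assessment is Cohen's d between arms at each two-week interval relative to baseline, with baseline to week 8 as the primary comparison. Formal tests are added: unpaired two-sided t-tests, or under strong non-normality a "non-parametric Wilcoxon signed rank test) of the means at relevant time points". That sentence mentions neither change nor the arms. One of the two routes to declaring a possible effect is then "Clinically and statistically significant effects for changes in cytokines of interest".

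**Section 20a, laboratory subsection.** Means and confidence intervals are presented for the change in each group and for the between-group difference. Significance is tested by an unpaired t-test, with the same signed-rank fallback, "of the mean values for XN compared to placebo". An earlier sentence describes unpaired t-tests of means from baseline to each time point.

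**The concern.** A mean at a time point is, on its face, a mean level. An analyst who follows the formal-test sentence literally would compare week-8 TNF-alpha levels between arms, while section 14, the effect size and the evidence rule all refer to change.

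Three things are at stake:

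- **Power.** The stated figure applies to change. A test on levels has a different standard deviation and so a different power.
- **Coherence of the report.** A d on change, or an interval for change, beside a p-value on levels describes two quantities and can point two ways.
- **Freedom of choice.** The text can be read as between-arm change, between-arm level or, from the earlier laboratory sentence, baseline against follow-up with the pairing ignored. A choice among these made after the data are seen weakens the p-value.

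A level comparison also carries any chance baseline difference between two arms of 12 in full. The only adjustment in section 20b is a conditional ANCOVA on baseline CDAI, not on the baseline marker.

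**Working it through.** **Inputs from section 14.** Mean change -0.5 (XN) and 0.1 (placebo), so the difference is 0.6 pg/ml. The 0.25 pg/ml is taken as the SD of change. Two-sided alpha 0.05, 12 per arm. "Will we randomize up to 32 participants to allow for attrition up to 25" percent gives 32 × 0.75 = 24 in total, which agrees with 12 per arm.

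**Not in the document.** The SD of TNF-alpha level and the baseline-to-week-8 correlation, rho. I assume equal SDs at the two visits and vary rho.

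**Step 1: reproduce the stated power (test of change).**

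Noncentrality = difference / (SD × √(2/n)) = 0.6 / (0.25 × √(2/12)) = 0.6 / 0.1021 = 5.88, with 22 degrees of freedom.

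Noncentral-t power = 99.99% (normal approximation 99.996%). The claim of more than 90% is correct as a lower bound; 5 per arm would already give 91%.

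**Step 2: the same true effect tested on week-8 levels.**

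Randomization makes expected baselines equal, so the expected difference stays 0.6. With equal visit SDs, SD of change = SD of level × √(2(1 − rho)). Hence SD of level = 0.25 / √(2(1 − rho)). For example, at rho 0.9 this is 0.25 / √0.2 = 0.559, and noncentrality = 0.6 / (0.559 × 0.4082) = 2.63.

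| Assumed rho | SD of level (pg/ml) | Power of level test, 12 per arm |
|---|---|---|
| 0.3 | 0.211 | rounds to 100% |
| 0.5 | 0.250 | 99.99% |
| 0.7 | 0.323 | 99.2% |
| 0.8 | 0.395 | 94.4% |
| 0.85 | 0.456 | 86.8% |
| 0.9 | 0.559 | 71.0% |
| 0.95 | 0.791 | 42.8% |

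With no attrition (16 per arm), the level test has 94.9%, 83.6% and 54.7% at rho 0.85, 0.9 and 0.95.

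**Step 3: where the level test drops below 90%.** At 12 per arm, 90% power requires a level SD of at most about 0.433 pg/ml. The matching correlation is rho = 1 − 0.25² / (2 × 0.433²) = 0.83. At rho 0.5 the two SDs are equal; below that the level SD is the smaller and the level test is not the weaker one.

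**Step 4: effect size beside the p-value.** On change, the section 14 assumptions imply d = 0.6 / 0.25 = 2.4. On levels at rho 0.9 the standardized difference is 0.6 / 0.559 = 1.07. A d on change and a p-value on levels therefore do not describe the same comparison.

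**Laboratory subsection.** Section 14 gives no power for mean laboratory values (its safety calculation is on proportions), so no stated power is at issue. The point is only that the interval and the test should concern one quantity.

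**Fallback test.** The signed-rank test is for paired or one-sample data. The comparison is between two independent arms, for which the rank-sum test is the counterpart of the unpaired t-test.

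**The case against.** The strongest reply is that change was plainly meant. The cytokine paragraph opens on changes in cytokines, defines its comparison relative to baseline, and applies its significance criterion to changes; the t-test is the only formal test described up to that point. In the laboratory sentence, the test follows directly on intervals for change, so its mean values can be taken as mean changes. A reader might infer that the protocol tests a different endpoint from the one it powered. The documents do not establish that, and this part of the reply stands.

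A reader might also infer that the test lacks its stated power. That is not shown either: across much of the plausible range of correlation a level test also exceeds 90%, and the protocol gives no figure that places TNF-alpha above the threshold.

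The reply is also right on weight. Cytokines are secondary outcomes, the results are labelled preliminary, Cohen's d leads, and a mixed model with repeated time points is planned as well. No primary safety conclusion turns on this sentence.

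Two parts do not stand. The choice of test variable might be left to a statistical analysis plan, but here the protocol does state a test, and its words do not match its own sample-size basis. Context also does not settle the matter: the laboratory sentence uses change for one quantity and values for another, and the level wording appears in both subsections.

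**Conclusion.** The point holds as a defect of wording with a possible, not a demonstrated, cost in power. Followed as written, section 20a tests visit levels; section 14, Cohen's d and the evidence rule concern change from baseline. Change was probably intended, but the stated test does not say so.

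The power of more than 90% is secured only for change. On levels it would be lost only if the correlation exceeds about 0.83 (level SD above about 0.43 pg/ml). These figures rest on the protocol's own difference and SD of change, equal SDs at both visits, and normally distributed data. The case for change is that it gives the test, the effect size, the interval and the sample size one endpoint, not that it is always the more powerful analysis.

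The signed-rank fallback is wrong for a two-arm comparison on either reading.

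**What to change.** In the cytokine subsection of section 20a, state that the unpaired two-sided t-test compares within-person change from baseline between XN and placebo, with baseline to week 8 as the primary comparison. In the laboratory subsection, state likewise that the between-arm test is on change from baseline, the quantity for which the intervals are given. In both, name the Wilcoxon rank-sum test, applied to the changes, as the fallback under strong non-normality.

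The cost is a few words in two paragraphs. No extra data, visits, participants or analyses are needed, and the TNF-alpha power calculation can stay as it is.

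### The supplementary trend tests in section 20a do not isolate a difference between arms, so a change shared by XN and placebo could be taken as an XN effect or toxicity signal

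*Protocol*

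**What the plan says.** Both relevant paragraphs are in Protocol section 20a.

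**Markers** (inflammatory cytokines, gut permeability, endotoxemia). The principal assessment compares the arms. It is Cohen's d, described as a "statistic between XN- and placebo-treated groups at each 2-week interval compared to baseline, with the primary comparison being between baseline and week 8", and is accompanied by unpaired t-tests. Two findings count as evidence of a possible effect. The first is worded "Clinically and statistically significant effects for changes in cytokines of interest and/or" and the second is a d above 0.5. A separate trend analysis follows, in which overall increases or decreases are "tested for linear trends of the means by linear mixed ANOVA with time point as a repeated factor. Trends will be considered significant" on this rule: "Trends will be considered significant if p<0.05 for the model overall".

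**Laboratory safety measures.** Newly abnormal percentages are "compared between XN and placebo groups by Fisher's exact test". Changes are reported with a confidence interval for the difference between groups and tested by unpaired t-tests of XN against placebo. A trend analysis follows with the same time-only mixed ANOVA. Its result is one "which may be suggestive of evidence for cumulative toxicity if trending in a clinical deleterious direction". No p-value rule is given for it.

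Neither trend paragraph names arm or an arm-by-time term.

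**The concern.** Section 8 describes a randomized, placebo-controlled trial. In such a trial, evidence that XN changes a marker or harms a laboratory value is a difference between arms in change over time. The stated trend criterion does not test that, on either reading of the model:

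- If the model contains time only, its p-value tests drift pooled over both arms.
- If arm is also included, the whole-model p-value combines time, arm and interaction, and a shared drift alone can make it small.

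A shared drift is possible. Section 10 requires a CDAI above 150 at entry, so regression to the mean in disease activity can occur in both arms, and repeated visits and permitted concomitant medication act on both arms.

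Two interpretations are at stake. For the markers, the first evidence criterion names no arm contrast, so a significant pooled trend could be taken to meet its statistical part. For the laboratory values, the trend model is the only analysis that the paragraph links by name to cumulative toxicity, and Table 1 lists safety and tolerability as the primary outcome.

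**Working it through.** **1. The plan's nearest figure.** The protocol gives no power or error rate for the trend test. The closest figure is for TNF-α change in section 14: "n=24 allows for n=12 per arm and provides >90% power, at a significance threshold" of 0.05, comparing -0.5 (SD 0.25) pg/ml on XN with a placebo value "based on an estimated mean change of 0.1 +/- 0.25 pg/ml from placebo".

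- Standardized difference: (0.1 + 0.5)/0.25 = 2.4.
- Noncentrality of the t-test: 2.4 × √(12/2) = 5.88 on 22 df, two-sided critical value 2.074.
- Power: 99.99%, consistent with the stated figure of over 90%.

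This supports the between-arm t-test and says nothing about the trend rule.

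**2. What a shared drift does to each test.** Inputs from the protocol: 12 evaluable participants per arm (section 14), so N = 24; five visits at weeks 0, 2, 4, 6 and 8 (Table 2); threshold 0.05. Assumptions not in the protocol: no arm difference, linear drift δ (in SD units) by week 8 in both arms, compound symmetry, within-person correlation ρ of 0.3 to 0.7.

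With time scaled as 0, 0.25, 0.5, 0.75, 1, the sum of squares about its mean is 0.25 + 0.0625 + 0 + 0.0625 + 0.25 = 0.625. The noncentrality for time is

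λ = N × δ² × 0.625/(1 − ρ).

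For δ = 0.5 this is 24 × 0.25 × 0.625/(1 − ρ) = 3.75/(1 − ρ), that is 5.36, 7.50 and 12.50 at ρ = 0.3, 0.5 and 0.7. The error df are (24 − 2) × 4 = 88. For arm-by-time, λ = 0 whatever δ is, because the drift is the same in both arms.

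The protocol does not say how time enters the model, so two forms are shown: visit as a five-level factor, tested jointly with arm-by-visit (8 df), and a pooled linear trend (1 df). Entries are the probability of p<0.05 from the noncentral F, with the simulated rate (20,000 trials per cell) in brackets.

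| δ = 0.5 SD, 12 per arm | ρ = 0.3 | ρ = 0.5 | ρ = 0.7 |
|---|---|---|---|
| Overall, visit as factor (8 df) | 29.2% (28.6%) | 41.0% (41.2%) | 66.1% (66.5%) |
| Pooled linear trend (1 df) | 62.9% (62.7%) | 77.3% (76.9%) | 93.8% (93.9%) |
| Arm-by-visit | 5% (4.9%) | 5% (5.1%) | 5% (5.2%) |
| Arm-by-linear-time | 5% (4.6%) | 5% (4.9%) | 5% (5.2%) |
| Week-8 change, t-test between arms | 5% (4.5%) | 5% (4.8%) | 5% (5.0%) |

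**3. Sensitivity to the assumed drift** (simulated, 12 per arm, ρ = 0.3 / 0.5 / 0.7).

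- No drift: every test is near 5%.
- 0.25 SD: overall test 9% / 12% / 17%; pooled linear trend 21% / 27% / 41%.
- 1 SD: overall test 91% / 98% / 100%; pooled linear trend 99.5% or more.

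**4. If all 32 are evaluable** (16 per arm, δ = 0.5 SD). The overall test rejects in 40% / 56% / 82% and the pooled linear trend in 76% / 88% / 98%. Retaining more participants raises these rates, while arm-by-time stays near 5%.

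**The case against.** The strongest reply is that the trend test does not carry the treatment claim. Its stated purpose is to look for overall increases or decreases, which is a question about time. The marker results are declared preliminary, the principal assessment is a between-arm effect size, and both paragraphs contain between-arm tests that a shared drift does not move. The drift is also assumed: selection is on CDAI, not on cytokines or on liver and renal values, so regression to the mean in those measures is indirect at most.

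Much of this stands, and it rules out three stronger readings that a reader might infer.

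- *That the plan would label any shared drift an XN effect.* The text calls the trend significant, without attributing it to XN. The opening for misreading is the first evidence criterion, which names no contrast.
- *That the whole-model rule also governs safety.* It is written for the markers only. The laboratory paragraph has the same model, no p-value rule, and cautious wording about toxicity.
- *That the marker or safety analysis as a whole is invalid.* Cohen's d, the t-tests, Fisher's exact test and the confidence interval for the difference all compare the arms.

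What the reply does not remove is that the protocol states a significance criterion which cannot show what a placebo-controlled trial is run to show. This is not a detail left to a statistical analysis plan: a plan that follows the rule inherits the problem, and one that departs from it contradicts the protocol. The longitudinal regression part of section 20a already judges by differing slopes, there according to XN metabolite status.

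**Conclusion.** The trend criterion is wrong as written for the markers, and the laboratory trend needs the matching clarification. It is a should-fix, because the analyses that carry the arm comparison are not affected.

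Under the assumed 0.5 SD shared drift with no arm difference and 12 per arm, the false-signal rate is roughly 30% to 65% with visit as a factor and roughly 60% to 95% for a pooled linear trend, against about 5% for arm-by-time. These are illustrations. They depend on drift size, correlation and model form, none of which the protocol gives, so no single rate should be quoted as the trial's error rate. With no drift the excess disappears. The direction does not depend on the choice: any nonzero shared drift pushes the time-based tests above 5% and leaves the arm-by-time test where it is.

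**What to change.** In both trend paragraphs of section 20a, specify a linear mixed model with arm, visit and arm-by-visit as fixed effects and participant as a random effect. Replace the whole-model rule for the markers with a statement that any XN effect is judged on the arm-by-time (or week-8 change) contrast with its 95% confidence interval. Apply the same contrast to any statement that a laboratory trend suggests XN toxicity. Within-arm trends over time may still be reported descriptively. Word the first evidence criterion for the markers so that it refers to a difference between arms.

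Further covariates are not needed to cure this point. The cost is about one sentence in each trend paragraph and a few words in the evidence criterion, with the same data and sample size. It should be done before group assignments are unmasked.
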